### 4. Analysis Populations

#### 4.1 Intention-to-Treat (ITT) Population

The ITT population will consist of all individuals who completed the baseline assessment and were allocated to either the intervention or control condition, independent of their subsequent engagement with any intervention components. This group will be used as the primary sample for assessing intervention effectiveness, aligning with a real-world evaluation approach that accounts for variations in actual participation.

### 5. Data Management and Quality Assurance

#### 5.1 Handling of Missing Data

Data will be collected through an online Qualtrics survey with required-response items and programmed skip logic to minimize missing data at baseline. Despite these measures, some missingness is expected across follow-up rounds due to participant drop-out or missed assessments. All missing values will be clearly coded in the dataset.

For analysis, we will examine differences between participants with complete and incomplete data. When missingness is substantial, multiple imputation (MI) or maximum likelihood (ML) methods will be applied under the missing-at-random (MAR) assumption. Sensitivity analyses using pattern-mixture models will be conducted to assess the robustness of this assumption. Complete-case analysis may be used when missing data are minimal.

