### 2.1.2 Data Collection

Data collection will occur at three time points: at baseline and again at 6 and 12 months of follow-up. During each assessment, participants will complete self-administered questionnaires on tablets or smartphones via the Qualtrics platform. For individuals assigned to the STOS group, HIV self-testing outcomes will be documented by a trained counselor and stored in an encrypted file with restricted access. Only the Principal Investigator (PI) and the Study Statistician will be authorized to view these data to maintain strict confidentiality.

All study data will be housed on secure institutional servers in encrypted, password-protected formats to ensure robust data security.

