### 2.1.3 Retention and Engagement Strategies

To ensure sustained participation throughout the follow-up period, the research team will implement continuous engagement measures using multiple digital communication channels, including the Zalo application, SMS, telephone calls, and support from community peer leaders. Participants will be contacted regularly to receive project updates, appointment reminders, and encouragement to take part in each data-collection round. Ongoing assistance will also be provided to help maintain participants' motivation and consistency in completing questionnaires. For the STOS group, follow-up communication will additionally ensure that participants receive their self-testing kits. These combined strategies are expected to achieve follow-up retention rates exceeding 80% at each assessment point.

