#### 2.4.2 Primary and Secondary Outcome Analyses

To evaluate the effects of the STOS intervention, two groups will be compared: the STOS group, who receive an HIV self-testing kit and complete the online questionnaires, and the control group, who complete the questionnaires only. The primary outcomes are the rate of HIV testing uptake and the rate of new HIV infections during the study period. The secondary outcomes include changes in sexual behaviors, mental health, and other psychosocial indicators over time. To assess the effects of the intervention across time points, Generalized Estimating Equations (GEE) models will be applied, using a log link function for rate outcomes and an identity link function for continuous outcomes. The models will include variables for study arm (STOS vs. control), time (follow-up round), and their interaction term (arm  $\times$  time) to estimate longitudinal intervention effects. Robust standard errors will be used to account for within-subject correlation due to repeated measures. The results will be presented as Rate Ratios (RRs or Incidence Rate Ratios, IRRs) with 95% confidence intervals (CIs) and p-values to indicate the magnitude and statistical significance of the observed effects.

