#### 3.3 Primary Outcome

- **HIV testing uptake:**

Proportion of participants who report having tested for HIV at least once within a 6-month period, based on STOS testing records and self-reported survey data.

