## 5.2 Data Cleaning and Preparation

After exporting the data from Qualtrics, the research team will conduct structured cleaning procedures using STATA command scripts to ensure accuracy and consistency. Key tasks will include identifying outliers, detecting logically inconsistent answers, checking the correctness of skip patterns, and verifying that numerical variables fall within acceptable ranges. Variables that depend on previous responses will also be reviewed to confirm internal coherence.

For the preparation of the analytic dataset, information from two sources will be combined: (1) the self-administered online questionnaires collected through Qualtrics, and (2) HIV self-testing outcomes obtained from participants in the STOS intervention group. These datasets will be harmonized before merging. To ensure accurate linkage across time points, participants will be asked to provide the same nickname or pseudonym during every round of data collection.

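### The SAP does not say how testing uptake is coded when a questionnaire is missed, and because test records exist only in the STOS arm, its missing-at-random analysis can overstate STOS uptake

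*Combined protocol and SAP*

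**What the plan says.** SAP 3.3 defines the only primary outcome in the SAP: "Proportion of participants who report having tested for HIV at least once within a 6-month period, based on STOS testing records and self-reported survey data".

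The record source covers one arm. SAP 5.2 merges the questionnaires with "HIV self-testing outcomes obtained from participants in the STOS intervention group". Protocol 2.1.2 says how those records arise: "For individuals assigned to the STOS group, HIV self-testing outcomes will be documented by a trained counselor". Protocol 2.4.2 describes the comparator as "the control group, who complete the questionnaires only". Protocol 2.1.1 gives controls a voucher for venue testing, but neither document names voucher use as outcome data.

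On missing data, SAP 5.1 expects some loss at follow-up. If it is substantial, "multiple imputation (MI) or maximum likelihood (ML) methods will be applied under the missing-at-random (MAR) assumption". Complete-case analysis is allowed when little is missing, and pattern-mixture models are planned as sensitivity analyses of the MAR assumption. Protocol 2.1.3 says the engagement measures are "expected to achieve follow-up retention rates exceeding 80% at each assessment point".

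Neither document says what value uptake takes when the questionnaire is missed, with or without a STOS record, or which variables enter the imputation.

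**The concern.** For a man who skips a round's questionnaire, a STOS record can supply only one answer: tested. If the two sources are merged and SAP 5.1 is then applied, testers among STOS non-responders are recovered and the other STOS non-responders stay missing. In the control arm all non-responders stay missing, whether or not they tested.

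Whether the STOS outcome is observed therefore depends on the outcome itself, in one arm, even when questionnaire response is unrelated to testing. An analysis that assumes MAR given arm and covariates takes an outcome-selected sample as representative. Complete-case analysis does the same. The ITT definition in SAP 4.1 settles who is included, not how the outcome is ascertained. The primary comparison could then favour STOS with no true effect, while the MAR analysis is presented as the handling of missing data.

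**Working it through.** The documents give no expected uptake, effect size or power, so there is no planned figure to reproduce.

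**Inputs from the documents.** 50 men per arm (Protocol 2; SAP 2). Retention above 80% per round (Protocol 2.1.3), so 20% missing is the upper end of what is planned for, or 10 of 50 men per arm.

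**Assumptions.** True uptake u is 40–60% and equal in both arms. A share d of questionnaires is missing at random. A share s of non-responders' tests in the STOS arm is on record. No questionnaire and no record is coded missing.

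**Formulas.**
- Observed STOS uptake = u(1 − d + ds) / (1 − d + dus)
- Observed control uptake = u
- Odds ratio under no effect = (1 − d + ds) / (1 − d), which does not depend on u

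**Results at d = 0.20.**

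| True uptake | All on record (s = 1) | Half on record (s = 0.5) | None on record (s = 0) |
|---|---|---|---|
| 40% | 0.40/0.88 = 45.5% (+5.5) | 0.36/0.84 = 42.9% (+2.9) | 40% (0) |
| 50% | 0.50/0.90 = 55.6% (+5.6) | 0.45/0.85 = 52.9% (+2.9) | 50% (0) |
| 60% | 0.60/0.92 = 65.2% (+5.2) | 0.54/0.86 = 62.8% (+2.8) | 60% (0) |
| Odds ratio | 1.00/0.80 = 1.25 | 0.90/0.80 = 1.125 | 1.00 |

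In counts, with u = 50% and s = 1: 40 responders (20 tested) plus 5 record-only men give 25/45 = 55.6% in STOS, against 20/40 = 50% in control. The odds ratio is (25/20)/(20/20) = 1.25.

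At d = 0.10 and s = 1 the odds ratio is 1/0.90 = 1.11, and the bias is 2.5 to 2.6 points (for example 0.50/0.95 = 52.6%).

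**False positives.** Simulated trials with no effect, 50 per arm, one round, two-sided 5% test, d = 0.20:
- Pooled two-proportion test: 8.0–8.2% if all tests are on record and about 6% if half are, against 5.1–5.2% without recovered records.
- Unpooled test: 8.7–9.2% if all are on record, against 5.6–6.0% without recovered records.
- At d = 0.10 the pooled test rejects at most 5.9%.

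**Other codings in the same null case (d = 0.20).**
- Missing counts as not tested in both arms, all STOS tests recorded: STOS reads u and control reads 0.8u. The gap is 0.2u, or 8, 10 and 12 points at 40, 50 and 60% uptake.
- No record counts as not tested in the STOS arm only: no bias if every test is recorded. If half are, STOS reads 0.9u, which is 4 to 6 points too low.
- Imputation conditional on record status (u = 50%, s = 1 in all STOS men): no-record responders are all untested, so the 5 no-record non-responders are imputed untested, giving 25/50 = 50%. If half of all STOS tests are recorded, 10 of 30 no-record responders tested. The 10 non-responders then comprise 2.5 with a record and 7.5 without, of whom 7.5 × 1/3 = 2.5 are imputed tested. The total is (20 + 2.5 + 2.5)/50 = 50%.

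**The case against.** The strongest reply is that the coding behind these figures is not written down. SAP 3.3 speaks of men who report a test, and SAP 5.2 could be read as attaching records only to completed questionnaires. In that case the problem does not arise. A reader might infer that the SAP prescribes tested-if-record, missing-if-not. It does not. That is the ordinary result of merging the sources and applying SAP 5.1, and other codings remove or reverse the bias. But the sole SAP primary result should not turn on an unstated rule.

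Four further points stand in part:
- The share on record may be low. Protocol 2.3.1 describes follow-up questionnaires and STOS sessions together, and Protocol 2.3.2 names being unreachable as a common reason for discontinuation. Men who miss a round may also miss the session, although one held earlier in the window would be recorded. The all-on-record figures are an upper end.
- SAP 5.1 does plan to test MAR with pattern-mixture models. These are sensitivity analyses with no arm-specific assumptions stated, so they leave the primary estimate as it is.
- A reader might infer that no MI or ML model could remove the bias. That is too strong: conditioning on record status can restore MAR if response is random given that status. The SAP does not specify this.
- Inflation need not be confined to STOS. If non-responders test half as often in both arms (60% against 30%, 20% missing, all on record), STOS is overstated by 8.8 points and control by 6.0. The one-arm mechanism accounts for the difference of 2.8.

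The bias is also small beside sampling error. At 45 and 40 observed men and 50% uptake, the 95% half-width is 1.96 × √(0.25/45 + 0.25/40), about 21 points.

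**Conclusion.** The point holds as a risk created by an unstated coding rule, not as proof that STOS uptake will be inflated. On the ordinary reading of SAP 3.3, 5.1 and 5.2, complete-case analysis, or MI or ML that does not condition on record status, can favour STOS when there is no effect. At 20% missing at random and 40–60% uptake, the bias ranges from 0 to 5.6 points (odds ratio 1.00 to 1.25), according to how many non-responders' tests are on record. The documents do not allow that share to be estimated. The effect on the false-positive rate is moderate, and the simulations cover a single round rather than the full GEE model. It still merits correction before analysis, because it affects the SAP's only primary outcome, the error runs toward the intervention, and the planned primary analysis does not remove it.

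**What to change.** Add to SAP 3.3 and 5.1: *In the primary analysis, uptake at a round is observed only if the participant completed that round's questionnaire, in both arms. A STOS record without a questionnaire is treated as missing, as is a control without a questionnaire.* Apply MI or GEE after this rule.

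In addition:
- Report record-only STOS men as a count by round, and use them only in a labelled sensitivity analysis. Imputation conditional on record status is one suitable form.
- Specify the pattern-mixture assumptions separately by arm.
- Do not make missing-equals-not-tested in both arms the primary rule.
- State whether a record overrides the questionnaire among completers. This is a separate choice and does not affect the missingness mechanism.

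The cost is a few sentences. At 20% missing and 40–60% uptake, 10 × u = 4 to 6 record-only STOS observations per round are set aside if all tests are on record, and fewer otherwise. The rule removes the differential bias only if questionnaire response is unrelated to testing, or related to it equally in both arms. The arm-specific pattern-mixture analysis should probe that condition.

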## 5.2 Data Cleaning and Preparation

After exporting the data from Qualtrics, the research team will conduct structured cleaning procedures using STATA command scripts to ensure accuracy and consistency. Key tasks will include identifying outliers, detecting logically inconsistent answers, checking the correctness of skip patterns, and verifying that numerical variables fall within acceptable ranges. Variables that depend on previous responses will also be reviewed to confirm internal coherence.

For the preparation of the analytic dataset, information from two sources will be combined: (1) the self-administered online questionnaires collected through Qualtrics, and (2) HIV self-testing outcomes obtained from participants in the STOS intervention group. These datasets will be harmonized before merging. To ensure accurate linkage across time points, participants will be asked to provide the same nickname or pseudonym during every round of data collection.

## 5.3 Variable Coding and Labeling

All variables will be coded and labeled according to a standardized data dictionary to ensure consistency across all study rounds. Dichotomous variables will use fixed coding (e.g., 1 = Yes, 0 = No), and Likert-scale items will follow predefined response categories. Maintaining uniform coding conventions will facilitate accurate interpretation, allow meaningful comparisons over time, and improve the reproducibility of the analyses.

# 6. Statistical Methods

## 6.1 Descriptive Analysis

Descriptive statistics will be used to summarize baseline characteristics and study variables, separated by study arm: the STOS intervention group and the control group. Statistical comparisons will be performed between these two groups to evaluate the effects of the STOS intervention over time. Categorical variables will be presented as frequencies and percentages, while continuous variables will be summarized as means with standard deviations (mean  $\pm$  SD) or medians with interquartile ranges (IQRs), depending on the data distribution.

## 6.2 Primary and Secondary Outcome Analyses

Generalized Estimating Equations (GEE) with appropriate link functions (e.g., logit for binary outcomes, identity for continuous variables) will be applied to assess intervention effects

over time. Each model will include study arm, follow-up time, and an interaction term to estimate differential changes between groups. Robust standard errors will be used to account for correlations within individuals. Person-time will also be calculated, and rate ratios with 95% confidence intervals will be reported.

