## 2. Study Design Overview

This study is a pilot randomized controlled trial (pilot RCT) using a longitudinal cohort design among young men who have sex with men (YMSM) aged 15–29 years, with a total of 100 participants equally allocated into two groups:

- STOS intervention group (n = 50)
- Control group (n = 50)

Participants will be followed for a period of 12 months, with data collection conducted at three times: baseline, 6 months, and 12 months of follow-up.

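### HIV testing uptake: the effect rests on arm × time with no primary visit or contrast named, and protocol and SAP differ on its scale

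*Combined protocol and SAP*

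**What the plan says.** SAP 3.3 defines the primary outcome as a proportion: whether a participant tested at least once in a 6-month period. It does not say which period.

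Protocol 2.4.2 words it as a rate: "The primary outcomes are the rate of HIV testing uptake and the rate of new HIV infections during the study period". It specifies GEE "using a log link function for rate outcomes and an identity link function for continuous outcomes", with arm, follow-up round and arm × time "to estimate longitudinal intervention effects", and adds: "The results will be presented as Rate Ratios (RRs or Incidence Rate Ratios, IRRs) with 95% confidence intervals (CIs".

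SAP 6.2 specifies GEE "with appropriate link functions (e.g., logit for binary outcomes, identity for continuous variables". On the model terms it says: "Each model will include study arm, follow-up time, and an interaction term to estimate differential changes between groups". The only effect measure it names is in its last sentence: "Person-time will also be calculated, and rate ratios with 95% confidence intervals will be reported".

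SAP 2 describes a 12-month follow-up "with data collection conducted at three times: baseline, 6 months, and 12 months of follow-up". SAP 7 allows alternative link functions among its sensitivity analyses. SAP 6.3 directs multiplicity adjustment to secondary outcomes and subgroups.

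**The concern.** Three things a reader needs for the primary result are left open or inconsistent.

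- **Contrast.** With time as a category, three rounds give two arm × time coefficients. Neither document picks one, a joint test or an average, or states how time is coded. The analyst could choose between visits after seeing the data, and the multiplicity text does not mention the visits of the primary outcome.
- **Role of baseline.** Neither passage says whether baseline is a level of the time term. Arm × time answers a different question in each case.
- **Scale.** The protocol's wording leads to a log link and a risk or rate ratio for uptake. The SAP's example leads to a logit link, whose natural output is an odds ratio. No passage mentions an odds ratio or a conversion to risks.

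At stake are the power of the main comparison in a trial of 100 people and whether the reported effect is the one a reader expects.

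**Working it through.** The documents give no expected 6-month uptake, effect size or power, so there is no stated figure to reproduce. Every uptake value below is an assumption. The value 23.5% is 100 − 76.5, from the never-tested figure in protocol 1.2; it serves only as a low starting point and is not a 6-month rate.

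**1. Visit and contrast.** If the 6- and 12-month effects were each tested at 5% without adjustment, the chance of at least one false positive would be up to 1 − 0.95² = 9.75% if the tests were independent, and less with positive correlation.

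**2. Illustrative data, 50 per arm.** Tested at baseline, 6 and 12 months: control 15, 22, 25; STOS 15, 37, 40.

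Direct 12-month comparison:
- RR = (40/50)/(25/50) = 1.60.
- Variance of log RR = (1 − 0.8)/(50 × 0.8) + (1 − 0.5)/(50 × 0.5) = 0.005 + 0.020 = 0.025, so SE = 0.158.
- 95% CI = exp(0.470 ± 1.96 × 0.158) = 1.17 to 2.18. The difference is 30 points (12 to 48).

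*Reading A: baseline is a level of time.* Arm × time adds baseline variance, less a covariance term for repeated measures.
- Log scale: 2 × (1 − 0.3)/(50 × 0.3) = 0.093 is added to 0.025.
- Logit scale: 2/(50 × 0.3 × 0.7) = 0.190 is added to 1/(50 × 0.8 × 0.2) + 1/(50 × 0.5 × 0.5) = 0.205.
- The baseline term is therefore nearly four times the 12-month term on the log scale, but about equal to it on the logit scale. This is why the link matters for the interaction.
- Fitted GEE, arm × time at 12 months: log 1.60 (0.86 to 2.99), p = 0.14; logit 4.00 (1.29 to 12.41), p = 0.016. The first is a ratio of risk ratios, the second a ratio of odds ratios.

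*Reading B: only 6 and 12 months enter.* Arm × time compares the 12-month effect with the 6-month effect.
- Log: 1.60/(37/22) = 1.60/1.68 = 0.95, p = 0.80.
- Logit: 4.00/3.62 = 1.10, p = 0.84.
- Uptake differs by 30 points at each visit (74% v 44%, then 80% v 50%), yet the interaction is null because the effect hardly changes. The arm term, here the 6-month effect, has p = 0.0039 (log) or 0.0028 (logit).

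**3. Simulation under Reading A.** 40,000 trials per scenario, 50 per arm, 6- and 12-month uptake equal, latent within-person correlation 0.3, independence working correlation with sandwich variance, two-sided 5% Wald test of arm × time at 12 months.

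| Control v STOS uptake, baseline to follow-up | Log | Logit | Links disagree |
|---|---|---|---|
| 23.5% flat v 23.5 to 30% | 8% | 9% | 1% |
| 23.5 to 40% v 23.5 to 50% | 8% | 11% | 3% |
| 30% flat v 30 to 50% | 29% | 35% | 6% |
| 23.5% flat v 23.5 to 50% | 43% | 53% | 10% |
| 30 to 40% v 30 to 65% | 31% | 48% | 17% |
| 30 to 50% v 30 to 80% | 31% | 68% | 37% |

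The fifth row gave 47% for logit on a rerun. With 40 per arm (80% retention) that row becomes 25% v 40%, with 15% disagreement.

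Power of the direct 12-month test in the last three rows, log v logit scale: 79% v 79%, 69% v 73%, 89% v 89%. Both links therefore gain from dropping the interaction.

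With no true effect, rejection is 4.3–4.8% (log) and 5.1–5.5% (logit).

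**The case against.** **The link is settled by the protocol.** This largely stands. Protocol 2.4.2 calls uptake a rate and gives rates a log link and RRs, and the SAP's logit is only an example. A reader might infer that no link is specified anywhere. The documents do not support that: they disagree, and following the protocol reconciles them.

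**SAP 6.2 contradicts itself.** A reader might infer this from a logit link beside rate ratios. The rate-ratio sentence sits with person-time and may concern only HIV incidence, which SAP 3.4 expresses per 100 person-years. This is therefore an ambiguity rather than a proven contradiction. On that reading, however, the SAP names no effect measure for its primary outcome. Nor does any passage plan to report an odds ratio as a rate ratio.

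**The large gaps come from large assumed effects and from including baseline.** This stands. Disagreement between links is at most 10% in the first four scenarios, and every figure in the table depends on Reading A. Reading B removes the dependence on link but leaves an interaction that does not test for an effect.

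**It is a pilot.** Aim 3 in protocol 1.4 is feasibility and acceptability, which softens the consequence. But protocol 2 and SAP 3.1 state an effectiveness aim, and protocol 2.4.2 promises p-values.

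**Conclusion.** The point holds, with the contrast as its main part and the link second. Both documents rest the effect on uptake on arm × time without naming a primary visit or contrast, and they need reconciling on scale.

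Under Reading A, the interaction has clearly less power than a direct comparison in the moderate and large scenarios where both were run: 31–68% against 69–89% in the two largest. Under Reading B it does not address whether STOS works.

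A reader might infer that the choice of link alone will decide the trial or inflate false positives. The calculations do not support this. With equal true baseline uptake, which randomisation gives on average, the two nulls coincide and error is about 5% under both links. A direct comparison expressed as a risk ratio is also essentially the same from either link: identical under independence working correlation, and within 3.1% under exchangeable correlation.

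The sizes rest on assumed uptake, a latent correlation of 0.3 and equal uptake at 6 and 12 months. That no visit or contrast is named rests on the text alone. This is a cheap improvement worth making, not a defect that invalidates the trial.

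**What to change.** Use matching text in SAP 6.2 and protocol 2.4.2:

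- **Primary contrast.** Compare STOS with control directly on uptake at one named follow-up visit, or as one named average of the 6- and 12-month visits, stating how the average is taken. The average fits the six-monthly testing aim in SAP 1.2.
- **Model.** One GEE with categorical time and the log link the protocol already names (Poisson family, robust standard errors, no person-time offset). State whether baseline is a level of time.
- **Effect measure.** Risk ratio with 95% CI. A risk difference is optional.
- **Arm × time.** Make it secondary, labelled as a ratio of risk ratios (log) or of odds ratios (logit).
- **Sensitivity.** Name logit as the alternative link under SAP 7.
- **Person-time and IRRs.** Reserve them for HIV incidence.

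The cost is text in two sections and a post-estimation contrast in Stata, with no new data. The downside is that the interaction both documents specify becomes secondary. The visit and link must be fixed before the data are analysed.

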#### 2.4.3 Multiple Comparisons and p-value Adjustment

When multiple comparisons are made, such as in subgroup analyses or secondary outcomes, adjustments to p-values will be considered to control for the risk of type I error. Methods such as Bonferroni correction or false discovery rate (FDR) adjustment will be applied as appropriate.

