### 3. Study Objectives and Endpoints

#### 3.1 Primary Objective

To evaluate the effectiveness of the STOS intervention in increasing access to and uptake of HIV testing among young men who have sex with men (YMSM).

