### 6.3 Multiple Comparisons and p-value Adjustment

For secondary outcomes and subgroup analyses involving several statistical tests, adjustments for multiple comparisons will be applied as appropriate. Methods such as Bonferroni correction or false discovery rate (FDR) procedures will be considered to control the risk of type I error.

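### The arm-by-time interaction is the stated effect estimate, with no baseline covariate and no named primary contrast; a baseline-adjusted arm effect at the same round is more efficient

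*Combined protocol and SAP*

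**What the plan says.** SAP 6.2 plans GEE models with a logit link for binary outcomes and robust standard errors. On the terms it says: "Each model will include study arm, follow-up time, and an interaction term to estimate differential changes between groups". Protocol 2.4.2 agrees: "The models will include variables for study arm (STOS vs. control), time (follow-up round), and their interaction term". It uses the interaction to estimate the effect over time. Neither section lists the baseline value or any other covariate.

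The primary outcome in SAP 3.3 is "Proportion of participants who report having tested for HIV at least once within a 6-month period", with no round stated. SAP 2 has three rounds: baseline, 6 and 12 months. No section says how time is coded, whether baseline enters as an outcome row, or which coefficient is the primary result.

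The multiplicity text does not settle it. Protocol 2.4.3 says "When multiple comparisons are made, such as in subgroup analyses or secondary outcomes, adjustments to p-values will be considered". SAP 6.3 says "For secondary outcomes and subgroup analyses involving several statistical tests, adjustments for multiple comparisons will be applied as appropriate". SAP 7 allows alternative model specifications, which adds freedom.

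**The concern.** There are two linked points.

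- **Efficiency.** Randomisation makes the arms equal at baseline in expectation. The interaction still subtracts the chance baseline difference at full weight, even when baseline predicts follow-up only weakly. Adjusting for baseline subtracts only the part that baseline predicts. With 100 participants, that loss of precision means wider intervals and a greater chance of missing a moderate rise in testing.
- **No named contrast.** The 6-month, 12-month, joint and linear interactions are all compatible with the text, so two statisticians following it could report different primary p-values. If the time variable is read as the 6- and 12-month rounds only, the interaction tests merely whether the effect changes between them, and nothing says that the arm term is then the result.

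The trial is a pilot, and Aim 3 of the protocol concerns feasibility and acceptability, so power carries less weight than in a confirmatory trial. But SAP 3.1 states the primary objective as "To evaluate the effectiveness of the STOS intervention in increasing access to and uptake of HIV testing", and protocol 2.4.2 promises p-values.

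**Working it through.** **Inputs from the documents.** 50 per arm (protocol 2; SAP 2); three rounds; retention expected above 80% per round (protocol 2.1.3), so 20% missing is used; logit link and robust standard errors (SAP 6.2).

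**Assumptions.** The plan has no power calculation to reproduce. Testing rates, effects and correlations below are assumed, as is a two-sided 5% level.

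**Closed form.** Take equal variances and a common correlation r between rounds, in units of 2σ²/n.

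- One follow-up round: interaction 2(1 − r); baseline-adjusted 1 − r². Ratio adjusted/interaction = (1 + r)/2.
- Mean of 6 and 12 months: interaction (1 + r)/2 + 1 − 2r = 3(1 − r)/2; adjusted (1 + r)/2 − r² = (1 − r)(1 + 2r)/2. Ratio = (1 + 2r)/3.

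Both ratios are below 1 for every r below 1. Latent correlations of 0.3 to 0.7 correspond to binary r of about 0.17 to 0.48:

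- one round: (1 + 0.17)/2 = 0.585 to (1 + 0.48)/2 = 0.74
- average: (1 + 0.34)/3 = 0.45 to (1 + 0.96)/3 = 0.65

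**Simulation on the logit scale.** Correlated binary data, 20% missing independently per follow-up round, exchangeable GEE, Wald tests, 2,000 trials per scenario (Monte Carlo standard error at most 1.1 points). Power (%) is interaction v baseline-adjusted. Each cell gives latent correlation 0.3 / 0.5 / 0.7.

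| Baseline; follow-up control v STOS | 12 months | Average of 6 and 12 months |
|---|---|---|
| 40%; 50% v 70% | 34/38/44 v 46/49/53 | 46/49/58 v 70/70/73 |
| 40%; 50% v 75% | 49/55/65 v 66/69/75 | 63/70/77 v 90/89/91 |
| 25%; 35% v 60% | 40/48/55 v 63/68/73 | 52/59/66 v 86/87/88 |
| 40%; 50% v 85% | 83/87/91 v 94/95/97 | 93/96/98 v 100/100/100 |
| 40%; 50% v 90% | 93/96/98 v 99/99/100 | 98/100/99 v 100/100/100 |

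For gains of 20 to 25 points, the like-for-like loss runs from 52.9 − 43.5 = 9 to 63.1 − 40.1 = 23 points at 12 months, and from 91.0 − 77.4 = 14 to 86.4 − 52.1 = 34 points for the average. For 50% v 85% it is 6 to 11 and 2 to 6 points. For 50% v 90% it is 2 to 6 and at most 2 points.

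**Time course.** Baseline 40%, control 50%. Power (%), range over the three correlations:

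| STOS gain at 6, 12 months | 12-month interaction | Adjusted 12-month | Adjusted average |
|---|---|---|---|
| 0, +25 | 47–63 | 66–75 | 33–36 |
| +10, +25 | 49–64 | 66–75 | 59–63 |
| +25, +10 | 12–16 | 15–19 | 60–63 |

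The adjusted test beats the interaction at the same round throughout. Which round or average is stronger depends on when the benefit appears.

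**No true effect.** Each single interaction rejects in 4.6 to 6.4% of trials and each adjusted test in 4.1 to 5.8%. Taking the smallest of four p-values gives 10.5 to 11.8% for interactions and 10.5 to 12.3% for adjusted tests. The inflation comes from leaving the contrast open, not from the interaction.

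**Follow-up rounds only.** With a constant 25-point effect, the interaction rejects in 5 to 6% of trials and the arm term in 61 to 66%.

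**Scale.** At 50% v 75% the marginal odds ratio is (0.75/0.25)/(0.50/0.50) = 3.0. The baseline-adjusted odds ratio has a median of 3.17/3.46/4.15, because it is conditional. A standardised risk difference averages 0.249 to 0.253 (true 0.25), with 93 to 95% coverage and power of 68/72/77% at 12 months and 90/89/92% averaged. It rejects in 5.2 to 6.1% of null trials.

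**Missing follow-up.** If rounds are missed independently, 0.2 × 0.2 = 4% have no follow-up data; if the same people miss both, 20%. In the second case (50% v 75%, correlation 0.3 and 0.7), average-contrast power is 61 v 87% and 77 v 89%. Multiple imputation of the adjusted average (1,000 trials) gives 88% and 87%, against 89% and 87% on available cases. Null rejection is 6.8% and 6.3%, against 6.4% and 5.9%.

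**The case against.** The strongest reply is that the planned interaction is valid when baseline is modelled, so the first point concerns precision in a pilot with no power target. The size of the loss rests on assumed rates. Kits are delivered and sessions scheduled (protocol 2.1.1), so a large effect is plausible, and then little is lost. A high within-person correlation also shrinks the gap: at latent 0.85 (baseline 40%, then 50% v 75%), power is 74 v 82% at 12 months and 86 v 94% averaged. Wording about differential change across three rounds favours baseline as a modelled round, so the follow-up-only reading is less likely. Picking the smallest of four p-values is a worst case.

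All of that stands as a limit on size. It does not alter the direction, which holds for every correlation below 1, nor the fact that no section names the contrast.

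A second reply is that a simpler model suffices: keep baseline as an outcome round and drop the arm main effect, so that the arms share one baseline mean. That is correct. For 40%, then 50% v 75%, it gives 68/71/77% at 12 months and 90/90/91% averaged, against 68/70/77% and 90/90/92% for covariate adjustment in the same run. Its odds ratio is marginal, and people with baseline data only stay in the model. It is an equally good remedy. Because the model as written includes an arm term, it does not impose this constraint, so the result confirms the loss.

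**Conclusion.** The concern holds. The plan uses the arm-by-time interaction without baseline adjustment and names no primary contrast. The issue is precision and an open choice of test, not bias, provided baseline is a modelled round. The direction of the efficiency loss is certain under equal variances and exchangeable correlation, and it appeared in every logit-link scenario with an effect at the tested round or rounds. The size is illustrative: 9 to 23 points of power at 12 months and 14 to 34 averaged for gains of 20 to 25 points, falling to 6 points or less for a 40-point gain. The change is worth making because it uses a round the trial already runs.

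**What to change.** Revise SAP 6.2 and protocol 2.4.2 together, before any arm-level outcome data are seen, or with a dated statement that the change came later.

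- **Contrast.** Name one primary contrast for testing uptake: a stated round, or the 6- and 12-month average. State that the average is stronger for a sustained effect and weaker if benefit appears only at 12 months. This is an estimand choice for the investigators.
- **Model.** Fit the GEE to the follow-up rounds with arm, categorical round and the baseline value of the same outcome. Add arm by round if a single round is primary; otherwise keep that term as descriptive. The model with a shared baseline mean is an acceptable alternative.
- **Reported effect.** After covariate adjustment, report a standardised marginal effect, fixing in advance whether it is a risk difference or a risk ratio. Reconcile the protocol's log link for rates with the SAP's logit in the same edit.
- **Missing data.** SAP 4.1 says "The ITT population will consist of all individuals who completed the baseline assessment and were allocated to either the intervention or control condition", so people with no follow-up data belong in the analysis. Apply to this model the SAP 5.1 provision that "multiple imputation (MI) or maximum likelihood (ML) methods will be applied under the missing-at-random (MAR) assumption". Standardisation and imputation were not simulated together, so check the combined error rate.
- **HIV incidence.** Report the planned person-time rate ratio without a baseline covariate or interaction. Protocol 2.1.1 does not invite people found HIV-positive, so there is no baseline value to adjust for. Protocol 2.4.2 lists new infections as primary and SAP 3.4 as secondary; that conflict must be settled separately.

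The cost is wording in two sections, with no added participants or visits. Committing to one contrast loses power if the effect follows another time course. The baseline questionnaire must contain the same six-month testing item; SAP 5.3 plans consistent coding across rounds, but the baseline items are not listed. Protocol 2.3.2 and 4 report some conduct in the past tense, so the trial may be well advanced and the timing of the change matters.
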